9.4.6. Physical Examination

A complete physical examination including all major body systems will be performed at Screening. At select subsequent study visits, an abbreviated review of systems will be performed to capture changes since Screening.

Height, weight and BMI will be determined as described in [Table 3](#).

9.4.7. C-SSRS

The Columbia Suicide Severity Rating Scale (C-SSRS) will be used to assess both behavior and ideation. The C-SSRS tracks all suicidal events, and provides a summary of suicidal ideation and behavior. It assesses the lethality of attempts and other features of ideation (frequency, duration, controllability, reasons for ideation, and deterrents), all of which are significantly predictive of completed suicide.

Two versions of the C-SSRS will be used in this study: the Baseline/Screening version (6 months and lifetime history) and the Since Last Visit version. The Screening version of the C-SSRS will be administered at Screening. The Since Last Visit version of the C-SSRS will be administered at all subsequent assessment times, as indicated in [Table 3](#).

The C-SSRS is to be administered by the Investigator or his/her qualified designee. Qualified designee is defined as physician, osteopath, nurse practitioner, clinical psychologist or physician's assistant, who is licensed and has completed the C-SSRS training within the last 2 years. The survey should be administered by the same assessor, where possible, throughout the study.

9.4.8. Injection Site Examination

CAM2038 injection sites will be examined during each scheduled visit for any signs of adverse site reactions, including erythema, pruritus, edema, pain, etc. If needed, a photograph of the adverse site reactions will be taken and shared with the medical monitor for review. The pain scale will be completed by the subjects within 10 minutes after each injection. The new injection site will also be examined within 15 minutes after each injection to determine if any site related AEs have occurred. Injection site evaluation forms will be included in the Trial MOP. Subjects will also be queried specifically about local tolerability AEs in connection to the examinations.

9.4.9. Psychosocial Counseling

All subjects will receive drug counseling once monthly (at least once every four weeks). Additional counseling can be provided as clinically indicated; however, all additional counseling, visits or phone calls must be recorded.

9.4.10. Treatment Identification Card

Subjects will receive a wallet card indicating that they are receiving BPN as part of the study. This card should be presented to health care providers by the subject in the event of an emergency or if medications such as opioid analgesics are required (see Section 8.7). Sample wallet cards will be provided for IRB submission.

9.4.11. Other Safety Considerations

Buprenorphine may impair the mental and physical abilities required for performance of potentially dangerous tasks. Subjects will be instructed to avoid operating heavy machinery during induction, and to exercise caution in performing activities requiring alertness such as driving a car during the first few days after the beginning of the trial, or until such time that they are reasonably certain that their ability to engage in such activities is not adversely affected.

9.5. Appropriateness of Measures

Standard safety outcomes, such as AEs, ECG, vital signs and clinical laboratory testing will be assessed during the study.

Given the open-label, uncontrolled nature of the study, the efficacy endpoints will be considered exploratory. These additional measures were selected as a series of measures and scales to provide an exploratory assessment of efficacy of CAM2038 q1w and q4w, including monthly urine toxicology with patient self-reported illicit opioid use, retention in treatment, Investigator- and subject-reported withdrawal and subject-reported cravings. Standard and widely used measures of withdrawal will be included in this study (COWS and SOWS) ([Handelsman et al, 1987](#); [Wesson and Ling, 2003](#)) in order to ensure that subject's withdrawal symptoms are adequately controlled by CAM2038 q1w and q4w. Desire to Use and Need to Use VASs was selected versus typical Craving VAS because the latter term is ambiguous and may have different meaning to different individuals, while the Desire/Need to Use VAS more directly assesses the potential behavioral outcome ([Kozlowski et al, 1989](#)).

9.6. Safety Variables

Safety variables include:

- AEs and SAEs
- Clinical laboratory tests
- ECG
- Vital signs
- Physical and injection site examinations
- Concomitant medications

9.7. Efficacy Variables

Efficacy variables include:

- Urine toxicology results for illicit opioids
- Self-reported illicit opioid use
- Retention (%) in treatment
- Work Productivity and Activity Impairment Questionnaire-General Health (WPAI-GH)
- EQ-5D-5L Health Questionnaire
- Patient Satisfaction Scale
- Measures of opioid withdrawal:
 - COWS
 - SOWS
- Measures of opioid craving:
 - Desire to Use VAS
 - Need to Use VAS
- Urine toxicology results for other drugs of abuse

10. DATA QUALITY ASSURANCE

This study will be conducted under Good Clinical Practice (GCP) and all applicable regulatory requirements. To ensure compliance, the Sponsor or designee may conduct a quality assurance audit, as outlined in Section 10.2.

Actions to ensure the accuracy and reliability of data include the selection of qualified investigators and appropriate study centers; the review of protocol procedures with the Investigator and study personnel prior to study start; the design of suitable source documents with appropriate instructions for use (where applicable); the internal audit of source data according to GCP and internal procedures to ensure their accuracy, completeness, and verifiability; as well as the periodic site monitoring by the Sponsor. The Sponsor or designee will review source documents for accuracy and completeness during on-site monitoring visits and after their return to the Sponsor; any discrepancies will be resolved with the Investigator, as appropriate.

Significant and/or repeated non-compliance will be investigated and remedial action instituted when appropriate. Failure to comply with remedial actions may result in investigational site termination and regulatory authority notification.

10.1. Data Collection

Source documents include but are not limited to original documents, data and records such as hospital/medical records (including electronic health records), clinic charts, lab results, participant diaries, data recorded in automated instruments, microfilm or magnetic media, and pharmacy records, etc. This study will use electronic data capture (EDC). At a minimum, all data required by the protocol should have supporting source documentation for entries in the EDC system.

All CRFs will be completed by the site staff prior to review by the Sponsor's monitor or designated representative. The Sponsor's monitor or designated representative will review all source records on-site and compare them to the data collected on the CRF. All entries, corrections, and alterations will be made by the Investigator or other authorized study personnel. All data entries will be verified for accuracy and correctness by independent monitors. The electronic data capture system maintains a full audit trail.

10.2. Study Auditing and Monitoring

Monitoring of the study site (including, but not limited to, reviewing CRFs for accuracy and completeness) will be performed by the Sponsor's designated monitor(s). The extent, nature, and frequency of on-site visits will be based on such considerations as the study objectives and/or endpoints, the purpose of the study, study design complexity, and enrollment rate. By signing the protocol, the Investigator agrees that, within local regulatory restrictions and institutional and ethical considerations, authorized representatives of the Sponsor, a regulatory authority, and/or an IRB may visit the site to perform audits or inspections, including the drug storage area, study

drug stocks, drug accountability records, participant charts and source documents, and other records related to study conduct. The purpose of the Sponsor audit or inspection is to systematically and independently examine all study-related activities and documents to determine whether the study-related activities were conducted, and data recorded, analyzed, and accurately reported according to the protocol, the site's standard operating procedures, GCP guidelines of the ICH, and any applicable regulatory requirements. The Investigator should contact the Sponsor immediately if contacted by a regulatory agency regarding an inspection.

11. STATISTICAL METHODS AND DETERMINATION OF SAMPLE SIZE

11.1. Statistical and Analytical Plans

Complete details of the statistical analyses to be performed will be documented in the Study Statistical Analysis Plan (SAP), which will be completed prior to unlocking the database. This document will include more detail of analysis populations, summary strategies, and any amendments to the proposed analyses listed here, if necessary. Any changes to the SAP will be outlined in the final study report.

11.2. Analysis Populations

The study analysis populations will consist of:

- **Full Exposure Safety Population:** All subjects who have been exposed to CAM2038 for 48 weeks
- **Overall Safety Population:** All subjects who received at least one CAM2038 treatment

The safety results will be presented for both Full Exposure Safety Population and Overall Safety Population.

11.3. Planned Analyses

11.3.1. Demographics and Other Baseline Characteristics

Disposition for all enrolled subjects will be summarized. Reasons for discontinuation will be tabulated.

Demographic data and baseline psychosocial characteristics will also be summarized.

Tabular summaries and/or listings will be provided for baseline clinical characteristics, such as illicit drug and treatment use history, medical and psychiatric history, inclusion/exclusion criteria, and medication history.

11.3.2. Analysis of Efficacy Measures

Exploratory efficacy measures will be summarized by visit using standardized descriptive statistics and listed by subject.

11.3.3. Analysis of Safety Assessments

Exposure and safety summaries will be presented for both Safety Populations.

All AEs will be coded by primary system organ class (SOC) and preferred term according to the Medical Dictionary for Regulatory Activities (MedDRA), and summarized by number and percent of subjects in each primary SOC and preferred term. Summaries of these AE subsets will

be presented for relationship to study drug, intensity, seriousness, AEs or SAEs leading to discontinuation and AEs occurring in 5% or greater (by preferred term). Frequencies for deaths and hospitalizations will also be summarized.

Data for clinical laboratory tests, ECG, vital signs, and physical and injection site examinations will be summarized using standard descriptive and change from baseline statistics. Shift tables and tabular summaries of abnormalities will be provided, where appropriate. Medications will be coded using the World Health Organization Drug dictionary and summarized using descriptive statistics.

By-subject listings will be provided for all safety data.

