In animal repeat-dose toxicity studies, CAM2038 q1w or FC vehicle formulation have been administered weekly for up to 6-months with no systemic toxicity associated with CAM2038 q1w or the FC injection depot vehicle observed. However, the long-term safety profiles of CAM2038 q1w and q4w in humans have not been described. In Study HS-13-487, pharmacokinetic profiles were evaluated for 4 repeat doses of CAM2038 q1w (one SC injection per week for 4 weeks) and one dose of CAM2038 q4w. In an upcoming parallel Phase III safety and efficacy study (HS-11-421), CAM2038 q1w and CAM2038 q4w will each be administered for up to 12 weeks (3 months). Therefore, the purpose of this study is to demonstrate the long-term safety of CAM2038 (q1w and q4w) as an office-based therapy for opioid maintenance treatment with BPN in patients with opioid use disorder.

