11.1.2 ADVERSE EVENTS

Each AE and serious adverse event (SAE) term recorded on the CRFs by primary system organ class (SOC) and will be mapped to a preferred term (PT) using the MedDRA dictionary. The Investigator will assess AE severity and relationship to the study treatment.

A treatment-emergent adverse event (TEAE) is defined as any AE with an onset date on or after the date of the first study treatment, or any ongoing event started on the date of the first dose that worsens in severity. Only AEs with an onset date prior to the date of the last dose + 30 days will be tabulated in summary tables. For the purpose of calculating treatment emergence and inclusion in summary tables, incomplete onset dates will be imputed as detailed in Appendix B.

AEs will be summarized by the number and percent of patients in each primary SOC and PT. Patients will be counted only once for each primary SOC and each PT. Summary tables of AEs by primary SOC, PT and intensity will be provided. If a patient has more than one AE coded to the same PT, the patient will be counted only once for that PT by using the event with the highest intensity. Similarly, if a patient has more than one AE within a primary SOC category, the patient will be counted only once in that SOC category by using the event with the highest intensity. AEs by primary SOC, PT and relationship to study drug will be provided as well. If a patient has more than one AE coded to the same PT, the patient will be counted only once for that PT by using the most related event. Similarly, if a patient has more than one AE within a primary SOC category, the patient will be counted only once in that primary SOC category by using the most related event. In addition, SAEs by primary SOC and PT will be provided. Deaths and SAEs will be summarized similarly to AEs. All AE tables will also include the total number of events, counting multiple events per patient.

Injection-related AEs, other (non-injection related) AEs as well as all AEs will be presented. Summaries of these AE subsets will be presented for the following categories:

- Study drug-related
- Intensity
- Serious
- AEs which led to treatment/study discontinuation
- SAEs which led to treatment/study discontinuation
- AEs occurring in 5% or greater of patients (by preferred term)

In the AE summary, the SOCs and the PTs within each SOC will appear in descending order of frequency.

Frequencies of deaths and hospitalizations will also be summarized.

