| TABLE 14.3.1.3 | Summary of CAM2038 Exposure by Dose and Number of Injections (Overall Safety Population) |
| TABLE 14.3.1.4 | Summary of CAM2038 Exposure by Dose and Number of Injections (Full Exposure Safety Population) |
| TABLE 14.3.2.1 | Summary of All Adverse Events by System Organ Class, Preferred Term, and Relationship (Overall Safety Population) |
| TABLE 14.3.2.2 | Summary of All Adverse Events by System Organ Class, Preferred Term, and Relationship (Full Exposure Safety Population) |
| TABLE 14.3.2.3 | Summary of All Injection-Related Adverse Events by System Organ Class, Preferred Term, and Relationship (Overall Safety Population) |
| TABLE 14.3.2.4 | Summary of All Injection-Related Adverse Events by System Organ Class, |

| | |
|------------------|--|
| | Preferred Term, and Relationship (Full Exposure Safety Population) |
| TABLE 14.3.2.5 | Summary of All Injection-Related Adverse Events by Preferred Term, Time to Onset and Duration (Overall Safety Population) |
| TABLE 14.3.2.6 | Summary of All Injection-Related Adverse Events by Preferred Term, Time to Onset and Duration (Full Exposure Safety Population) |
| TABLE 14.3.2.7 | Summary of All Non-Injection Related Adverse Events by System Organ Class, Preferred Term, and Relationship (Overall Safety Population) |
| TABLE 14.3.2.8 | Summary of All Non-Injection Related Adverse Events by System Organ Class, Preferred Term, and Relationship (Full Exposure Safety Population) |
| TABLE 14.3.3.1 | Summary of All Suspected to Be Drug-Related Adverse Events by System Organ Class and Preferred Term (Overall Safety Population) |
| TABLE 14.3.3.2 | Summary of All Suspected to Be Drug-Related Adverse Events by System Organ Class and Preferred Term (Full Exposure Safety Population) |
| TABLE 14.3.3.3 | Summary of All Injection Related Suspected to Be Drug-Related Adverse Events by System Organ Class and Preferred Term (Overall Safety Population) |
| TABLE 14.3.3.4 | Summary of All Injection Suspected to Be Drug-Related Adverse Events by System Organ Class and Preferred Term (Full Exposure Safety Population) |
| TABLE 14.3.3.5 | Summary of All Non-Injection Related Suspected to Be Drug-Related Adverse Events by System Organ Class and Preferred Term (Overall Safety Population) |
| TABLE 14.3.3.6 | Summary of All Non-Injection Suspected to Be Drug-Related Adverse Events by System Organ Class and Preferred Term (Full Exposure Safety Population) |

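### Apart from injection-related AEs, no planned AE table is split by time of onset, so the summaries of this long-term safety study do not separate start-of-treatment events from late ones

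*Protocol*

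**What the plan says.** Protocol 11.3.3 has AEs "summarized by number and percent of subjects in each primary SOC and preferred term". The subsets it then names are relationship, intensity, seriousness, discontinuation and the 5% cut. Time of onset is not among them.

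SAP 11.1.2 repeats the measure ("AEs will be summarized by the number and percent of patients in each primary SOC and PT") and sets the counting rule: "Patients will be counted only once for each primary SOC and each PT". It uses one window for all summary tables: "Only AEs with an onset date prior to the date of the last dose + 30 days will be tabulated in summary tables". AE tables also show the total number of events, again over the whole window.

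SAP Appendix A contains one exception, Table 14.3.2.5: "Summary of All Injection-Related Adverse Events by Preferred Term, Time to Onset and Duration (Overall Safety Population". Table 14.3.2.6 is the same table for the Full Exposure Safety Population. Neither Appendix A nor SAP 11.1.2 says whether time to onset runs from the first injection or from the injection before the event.

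Protocol 5.2 gives the reason for the study. Long-term safety in humans had not yet been characterized, and in the parallel Phase III study "CAM2038 q1w and CAM2038 q4w will each be administered for up to 12 weeks (3 months".

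**The concern.** What this study adds is safety information beyond the period that other studies cover. AEs are its leading safety endpoint, yet for every class except injection-related AEs the planned summary has no time axis. An event seen only in Week 1 and an event first seen in Weeks 25-48 produce the same table row.

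The denominator adds to this. In the Overall Safety Population every dosed patient stays in it, including those who left months before a late event could occur. With about 50% dropout expected, a late-onset AE looks rarer than it was among the patients still exposed.

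Elsewhere the SAP does use a time axis. Urine results are shown by week and month (10.1.2), retention by week (10.1.4), withdrawal scales by visit (10.1.6), and vital signs and the C-SSRS over time (11.1.4, 11.1.8). Exposure years (11.1.1) are given by dose and product but are not linked to AE counts by period.

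**Working it through.** **The plan's own figure.** Protocol 11.4 and SAP 7.0 give 228 enrolled, about 50% dropout and at least 100 patients with 48 weeks of exposure.
- 100/(1 - 0.5) = 200, so the simple inflation formula does not reproduce 228.
- 228 × 0.5 = 114 expected completers. Ending with exactly 100 would imply 1 - 100/228 = 56.1% dropout.
- So 228 includes a cushion. Nothing below depends on how it was chosen.

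**Which tables carry onset time (SAP Appendix A, Overall Safety Population).**

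| AE class | Table | Time of onset? |
|---|---|---|
| All AEs | 14.3.2.1 | No |
| Injection-related | 14.3.2.5 | Yes, origin undefined |
| Non-injection-related | 14.3.2.7 | No |
| Drug-related | 14.3.3.1 | No |
| SAEs | 14.3.6.1 | No |
| AEs leading to discontinuation | 14.3.7.1 | No |

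**Patients at risk over time.** The documents give no dropout pattern, so I assume two. Both reach 50% at Week 48, and all enrolled patients may complete (SAP 7.0). One patient-year is 52.18 weeks.

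*Constant hazard*, ln 2/48 = 0.01444 per week:
- On treatment after Week 24: 228 × 2^(-0.5) = 161.
- Patient-weeks: 2512 in Weeks 1-12, 2112 in Weeks 13-24 and 3270 in Weeks 25-48. The total is 7894, or 151 patient-years.
- Share in Weeks 25-48: 3270/7894 = 41%.

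*Front-loaded*, 25% lost linearly by Week 8 and a further 25% by Week 48 (228, then 171, then 114):
- On treatment after Week 24: 171 - 57 × 16/40 = 148.
- Patient-weeks: 8 × (228 + 171)/2 + 40 × (171 + 114)/2 = 7296, or 140 patient-years.
- In Weeks 25-48: 24 × (148.2 + 114)/2 = 3146 patient-weeks, or 60 patient-years.

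**Size of the understatement.** Take an AE with first onset after Week 24 in 11 patients.
- As planned: 11/228 = 4.8%.
- Of patients on treatment after Week 24: 11/161 = 6.8% (constant hazard) or 11/148 = 7.4% (front-loaded).
- The AE window stays open for 30 days (4.29 weeks) after the last dose. If the dropout time is the date of last dose, those still in the window at Week 24 are those still dosed at Week 19.71. This is 228 × exp(-0.01444 × 19.71) = 171.5, or 171 - 57 × 11.71/40 = 154.3. The percentages become 6.4% and 7.1%.

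**Same row, different timing.** Take 23 affected patients under constant-hazard dropout. The planned table shows 23/228 = 10.1% in every case. Expected events in a period are 23 × (its patient-weeks)/(patient-weeks over which the events are spread), ignoring depletion of those already affected. Each cell is that number as a percentage of patients on treatment at the start of the period.

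| Weeks | 1-4 | 5-12 | 13-24 | 25-36 | 37-48 |
|---|---|---|---|---|---|
| On treatment at start | 228 | 215 | 192 | 161 | 136 |
| All in Weeks 1-4 | 10.1% | 0 | 0 | 0 | 0 |
| Constant rate | 1.1% | 2.2% | 3.2% | 3.2% | 3.2% |
| All after Week 24 | 0 | 0 | 0 | 7.7% | 7.7% |

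In the last row the risk over Weeks 25-48 is 1 - (1 - 0.077)² = about 15%, against the tabulated 10.1%.

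**The case against.** Several points on the other side stand, and they limit the concern.

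- *Onset is not ignored.* A reader might infer that no AE is summarized by time of onset. Tables 14.3.2.5 and 14.3.2.6 do this for injection-related AEs in both populations. They may still not show late first occurrence if their clock restarts at each injection.
- *Timing is recoverable.* A reader might infer that the study cannot show when AEs arise. Onset and resolution dates are collected (Protocol 9.4.1.1), partial onset dates have an imputation rule (SAP Appendix B), and all safety data are listed by subject (Protocol 11.3.3). What is missing is a planned summary with a denominator. The closing line of SAP 11.1.2 on other analyses names none.
- *The Full Exposure tables are not diluted.* If completers have the same risk as others, 11 × 114/161 = 7.8 of the late cases fall among 114 completers, which is 6.8%. But these tables are still cumulative, and they omit patients who left early, including those who left because of an AE.
- *The 5% cut does little harm.* A reader might infer that a late AE at 4.8% disappears. It drops only from the common-AE tables and stays in Tables 14.3.2.1 and 14.3.4.1. Eleven is also the largest count below the cut, since 12/228 = 5.3%.
- *Some early effects are already excluded.* Withdrawal symptoms are not recorded as AEs (Protocol 9.4.1.1), which removes part of the start-of-treatment signal but not the rest.

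**Conclusion.** The point holds for all AEs combined, non-injection-related AEs, drug-related AEs, SAEs and AE discontinuations. The plan followed exactly gives one crude cumulative percentage for each, and that percentage does not distinguish early from late onset. In the Overall Safety Population it also understates late-onset AEs relative to patients still at risk: 4.8% against 6.8% to 7.4% in the illustration, or 6.4% to 7.1% if the 30-day tail is counted in the denominator. These sizes rest on the planned 228 and 50% and on assumed dropout shapes; the lack of an onset split does not depend on them.

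This is a gap in descriptive presentation. No test or estimate is invalid and no data are lost. It is worth correcting because late safety is the reason for the study and the correction is cheap.

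**What to change.** In SAP 11.1.2 and Appendix A:

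1. Add onset-period columns to Tables 14.3.2.1, 14.3.3.1, 14.3.6.1 and 14.3.7.1, and keep the cumulative column. Suitable periods are Weeks 1-4, 5-12, 13-24, 25-36, 37-48, and after Week 48 up to 30 days after the last dose. The last column is needed because weekly dosing can run to Week 48. Protocol 5.2 gives 12 weeks per product in the parallel study without saying whether the same patients take both. Breaks at Weeks 12 and 24 serve either case.
2. Classify each patient by first onset, counted from the first CAM2038 injection.
3. Use as denominator the patients whose AE window (treatment plus 30 days after the last dose) is still open at the start of the period, or the patient-time in that window. A denominator of patients on treatment would not match, because an AE shortly after the last dose would count in the numerator only.
4. Flag onset dates that Appendix B sets to the first dose, since these inflate the first column.
5. State the time origin for Tables 14.3.2.5 and 14.3.2.6.

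The cost is SAP wording and programming; no new data are needed. The tables become longer and the late columns will hold small counts. Columns by first onset show when an AE begins, not whether it persists; persistence would need a separate summary of duration.
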